### 3.5 Serial Monitoring Identifies Patients with Ultra-Low Risk GVHD

Given that the MAP can also act as a monitoring biomarker, we used both the clinical response and the MAP during the first two weeks of systemic steroid treatment to analyze 85 pediatric patients with Minnesota standard risk/AA1 GVHD. MAPs were categorized as high or low using the validated 0.29 threshold. Changes in clinical severity were scored as either response, stable, or progression. Patients who responded by the end of week one and maintained both clinical response and a low MAP at week two (48% of patients), experienced 95% day 28 ORR. Importantly, serial monitoring demonstrated that **slow** clinical responders (17% of patients) have equally good outcomes with a 100% ORR; these patients have stable disease at week one, a response at week two and a low MAP at all three assessments. The remaining patients (35%) either lacked a treatment response or had an increase in their MAP above 0.29. Taken together, serial monitoring identifies 65% of patients with Minnesota standard risk/AA1 GVHD as an **ultra-low risk** group with higher response rates (96% vs 47%, p<0.001) than other patients. Furthermore, GVHD flares that required an increase in treatment occurred in only 5% of patients with ultra-low risk GVHD. Thus, these patients are excellent candidates for a GVHD treatment strategy that minimizes steroid exposure.

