Although multiple tools have been developed for the assessment of PROs, the Center for International Blood and Marrow Transplant Research (CIBMTR) and the Blood and Marrow Transplant Clinical Trials Network (BMT CTN) have called for the harmonization of the use of PRO measures in HCT studies. The NIH PROMIS (Patient Reported Outcomes Measures Information System) tool is validated in HCT patients, free, and easy to administer and score. PROMIS tests quantify clinically meaningful changes and have been validated for use in children as young as 5 years when using parental proxy. In this study we will use PROMIS surveys to measure symptoms of poor QOL associated with steroid exposure (Global QOL, Physical Mobility, Anxiety, Depression, Fatigue, Sleep Disturbance). This trial will provide essential data lacking in the literature on HRQOL in children diagnosed with acute GVHD and treated with steroids. We will be able to analyze PROs as a function of steroid exposure, to further describe the impact of steroid use on HRQOL. Since measures within a PROMIS domain (such as physical or mental health) can be compared on the same t-score metric, regardless of number and items administered, this will allow for further use of this data for future comparisons across studies that may use different PROMIS measures.

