## **7.0 TREATMENT PLAN**

## 7.1 Treatment Dosage and Administration

**Table 1: Treatment Schema**

TX		Week 1			Week 2			Week 3***	Week 4	Cumulative mg/kg
MAP	mg/kg	MAP	Response	mg/kg	MAP	Response	mg/kg	mg/kg	mg/kg	
AA1	0.5	>0.29	All	1-2**	Ad lib or clinical trial					
			Progression							
		≤0.29	Responder	0.35	≤0.29	Responder	0.25	0.15	0.1	8.75 (↓68%)
						Partial loss of response*	0.35	0.25	0.15	10.9 (↓60%)
						Flare	1-2**	Ad lib or clinical trial		
AA1	0.5	≤0.29	Stable	0.5	>0.29	All				
					≤0.29	Responder	0.35	0.25	0.15	11.2 (↓59%)
						Stable	1-2**	Ad lib or clinical trial		
					>0.29	All				

\* partial loss of response = increase in GVHD stage from week 1 but less than baseline  
 \*\* suggested dose  
 \*\*\* partial loss of response, delay taper, refer to protocol section (section 7.1.9)

- 7.1.1 To avoid delays in treatment and because steroid treatment is the standard of care for GVHD, the starting prednisone dose of 0.5 mg/kg/day (or oral or intravenous equivalent) can start before screening is complete. The initial dose is based on its proven effectiveness as a starting dose for grade II GVHD. Dosing frequency can be daily or in divided doses as per institutional standard. For example, a patient who is diagnosed with Minnesota standard risk GVHD can begin prednisone treatment at 0.5 mg/kg/day pending Ann Arbor score results. If Ann Arbor 2/3 GVHD is confirmed, the patient will not be enrolled on the study, and the prednisone dose should be increased to 1-2 mg/kg/day and further treatment will be at physician discretion. If Ann Arbor 1 GVHD is confirmed, treatment should continue at the initial dose with further dose tapers or increases as specified in **Table 1**. In cases where treatment was not begun during

screening, treatment must begin within one day of confirmation of Ann Arbor 1 GVHD. Day 0 is the day that systemic treatment was begun.

- 7.1.2 Subsequent prednisone doses are determined based on the clinical response and MAPs as in **Table 1**.
- 7.1.3 Prednisone dose or equivalent can be rounded to nearest feasible dose based on formulation, dosing options, and institutional practice.
- 7.1.4 Prednisone dose is based on baseline weight.
- 7.1.5 Patients with an early and sustained response over all four weeks are tapered the most aggressively to 0.1 mg/kg/day by week 4.

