- 7.1.6 Prednisone dose remains 0.5 mg/kg/day for patients with stable GVHD and a favorable MAP at the first assessment (week 1) do not taper. Slow responders, i.e., patients with response by week 2, begin the taper at week 2.
- 7.1.7 Patients who do not respond by week 2 are removed from study treatment schedule and it is recommended that the prednisone dose be increased to 1-2 mg/kg/day in order to produce a clinical response.
- 7.1.8 Patients with an initial response at week 1 but a partial loss of response at week 2 (e.g., increase in GVHD staging from week 1 but still improved compared to baseline) do not taper further until staging improves.
- 7.1.9 For patients who have a partial loss of response at week 3, delay taper until further improvement in stage.
- 7.1.10 Patients whose GVHD worsens compared to baseline, fails to improve by week 2, or who develop a MAP >0.29 are removed from study treatment schedule and it is recommended that the prednisone dose be increased to 1-2 mg/kg/day with further tapering per physician judgment.
- 7.1.11 Physicians are permitted to increase steroid dosing whenever deemed in the best interest of the patient. The reason for increasing the steroid dose will be reported.
- 7.1.12 Prednisone dosing will be reported weekly through day 28 and then either weekly or whenever the dose is changed, whichever is less frequent, until study day 90. After week 4 prednisone tapering or dose increases will be determined by the treating physician.
- 7.1.13 To promote adherence to the steroid dosing schedule outlined in **Table 1**, the prednisone dose for the week will be communicated by the MAGIC DCC to the treating physician. For weeks 1 and 2 this communication will occur simultaneously with reporting of the biomarker results.
- 7.1.14 **GVHD Prophylaxis Medications**  
Medications given for GVHD prophylaxis such as cyclosporine, tacrolimus, sirolimus, methotrexate, mycophenolate should be continued at therapeutic doses (according to institutional standards) and adjusted as necessary for renal,

central nervous system (CNS) or other toxicity using institutional guidelines. This study allows for changes in GVHD prophylaxis medication (e.g., replacement of cyclosporine with sirolimus for management of posterior reversible encephalopathy syndrome [PRES]) as per institutional standards. GVHD prophylaxis medications will be tapered according to local institutional tapering practices.

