### **14.3 Data Analysis Plans**

The primary endpoint is the proportion of patients who (1) achieve CR, VGPR, or PR by day 28 of treatment without additional immunosuppressive therapy and (2) whose cumulative prednisone exposure is  $\leq 13.5$  mg/kg. The proportion of patients who are successfully treated with  $\leq 13.5$  mg/kg cumulative prednisone dose will be compared to the historical control rate of 14% using a Chi-squared test.

All study patients will be analyzed and when appropriate, subset analyses by ultra-low risk and other patients will be performed. We expect 33 ultra-low risk patients and 17 other patients out of our sample size of 50 study patients, which will be sufficient for subset analyses.

Secondary outcomes such as the overall response rate, duration of response, cumulative incidence of steroid-refractory GVHD, incidence of serious infections (viral, bacterial, fungal, and parasite), cumulative steroid exposure at day 28 and day 90, overall survival at 6 and 12 months, cumulative incidence of NRM at 6 and 12 months, relapse rate at 6 and 12 months, and cumulative incidence of chronic GVHD requiring systemic steroid treatment by one year will be estimated and compared to historical controls.

Continuous variables will be summarized using standard summary statistics such as number of observations (n), mean, standard deviation (SD), minimum and maximum values, median, and 1st and 3rd quartiles. Categorical variables will be summarized in frequency tables as counts and percentages.

Cumulative incidence of non-relapse mortality will be estimated by Gray's method and relapse will be considered as a competing risk. Disease free and overall survival, defined as the time from the transplantation to death or to last follow-up if alive, will be estimated by the method of Kaplan-Meier and the probability curves and 95% confidence intervals will be provided based on the method of Brookmeyer and Crowley.

The exploratory endpoints of linear growth velocity and patient reported outcomes as per Appendix B will be described for patients whose cumulative steroid exposure is  $\leq 13.5$  mg/kg and  $> 13.5$  mg/kg. Linear growth velocity will be expressed as a standard deviation score of the sex- and age-specific mean.

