Data from a randomized adult acute GVHD treatment trial suggests that QOL (both physical and mental functioning) diverges around day 90 among patients with different steroid exposures. We expect our measures to show greater and faster improvement in QOL in patients with less steroid exposure, but for completeness, we will track PROs until 180 days from GVHD onset. The day 180 time point may be confounded by steroid treatment for chronic GVHD in some patients, and subsets may thus need to be analyzed. Formal comparisons between groups are not planned but we will explore the possibility of creating groups according to cumulative steroid dose. If groups can be created, we will compare groups using the difference of half of a standard deviation (5 points) in PRO scores which has been validated as clinically meaningful. PROMIS instruments will be scored in accordance with the manuals ([https://www.healthmeasures.net/index.php?option=com\\_content&view=article&id=180&Itemid=994](https://www.healthmeasures.net/index.php?option=com_content&view=article&id=180&Itemid=994)) and the scores will be analyzed using generalized linear models. General hierarchical random effects linear mixed model will be employed with repeated measures nested within site to assess the change between groups in outcomes of interest across multiple time points. The model will also include a random intercept. Determination of model fit will be aided by diagnostics for model residuals. We expect that there will be some minor and major missing data. Minor missing data include missing values on individual survey items. Although we will endeavor to check all questionnaires upon their return and call the participants to try to complete missing items, some data may still be missing. These individual items will be imputed. The imputed values will then be used to obtain point estimates for the missing data. Since the proposed study is longitudinal, major missing data from participant attrition is more likely and, potentially, more problematic. Two different attrition strategies will be employed. In the first, a binary variable for dropout (Yes or No) will be created and we will develop a hierarchic logistic regression model for clustered data (hospital is the clustering variable) using generalized linear mixed models with a logit link function. Any demographic or medical variables identified during initial data screening predicting dropout will be entered first. In the next step, any PRO measures will be assessed as predictor of dropout. These analyses will address the generalizability of study results. Patient and parental proxy scores will be compared for the subsets where both scores are available (ages 8-17y). The QOL analyses will be conducted in collaboration with [name], co-investigator and an expert in the interpretation of pediatric PRO data at Emory University.

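### The planned quality-of-life contrast by steroid dose mixes GVHD course with steroid effect, because Table 1 assigns dose by response and MAP

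*Combined protocol and SAP*

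**What the plan says.** Section 14.3 says that growth velocity and PROs "will be described for patients whose cumulative steroid exposure is" at most 13.5 mg/kg and for those above it. It gives no time window for that split; the same threshold in the primary endpoint (4.4) covers the first four weeks.

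The PRO paragraph of 14.3 then does three things. It predicts a direction: "We expect our measures to show greater and faster improvement in QOL in patients with less steroid exposure". It says that no formal group comparisons are planned. It goes on to say that, if groups by cumulative dose can be formed, they will be compared on a half-SD (5-point) difference, and it describes a linear mixed model for change between groups. The model has repeated measures nested within site and a random intercept. No term for GVHD stage, response or MAP is named. The only confounding mentioned is steroid treatment for chronic GVHD at day 180.

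Section 3.6 gives the aim: "We will be able to analyze PROs as a function of steroid exposure, to further describe the impact of steroid use on HRQOL".

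On how dose arises, 7.1.2 says: "Subsequent prednisone doses are determined based on the clinical response and MAPs as in" Table 1. Under 7.1.10, patients whose GVHD worsens against baseline, "fails to improve by week 2, or who develop a MAP >0.29 are removed from study treatment schedule", with 1-2 mg/kg/day recommended. Under 7.1.11, "Physicians are permitted to increase steroid dosing whenever deemed in the best interest of the patient".

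**The concern.** A dose contrast can be read as a steroid effect only if the dose groups are otherwise alike. Here dose is set after baseline by the course of the disease, and 3.6 itself says that PROs pick up the burden of acute GVHD as well as of its treatment. Poor GVHD control can therefore raise the dose and worsen the score at the same time. The distortion runs in the direction that the plan predicts, so a difference in favor of low exposure would not show which cause produced it. The support cited in 14.3 for the prediction comes from a randomized adult trial, whereas exposure in this trial is not randomized.

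At stake is what can be concluded from a dataset that 13.3 describes as the first multicenter one of its kind in children with GVHD.

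**Working it through.** **1. Table 1 totals for children who stay on schedule.** Formula: 7 days × the sum of the four weekly doses.

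- Early responder: 7 × (0.5 + 0.35 + 0.25 + 0.15) = 8.75 mg/kg, as printed.
- Slow responder: 7 × (0.5 + 0.5 + 0.35 + 0.25) = 11.2 mg/kg, as printed.
- Partial loss of response at week 2: 7 × (0.5 + 0.35 + 0.35 + 0.25) = 10.15 mg/kg. Table 1 prints 10.9; holding 0.35 for one more week gives 10.85. The row and its total must be reconciled, but every version is below 13.5.
- Slow responder with a one-week delay under 7.1.9: 7 × (0.5 + 0.5 + 0.35 + 0.35) = 11.9 mg/kg.

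**2. Totals for children removed from the schedule.** Formula: dose already given + remaining days × daily dose. The 1-2 mg/kg/day is the plan's suggested range; a flat dose and weekly halving are assumptions.

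| Removed at | Already given | 1 mg/kg/day flat | 2 mg/kg/day flat | 1 mg/kg/day halved weekly |
|---|---|---|---|---|
| Week 1 | 3.5 | 3.5 + 21 = 24.5 | 45.5 | 15.75 |
| Week 2, after response | 5.95 | 5.95 + 14 = 19.95 | 33.95 | 16.45 |
| Week 2, after stable disease | 7.0 | 7.0 + 14 = 21.0 | 35.0 | 17.5 |

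**3. Where the cut falls.** On-schedule totals reach at most 11.9 mg/kg. Removed totals start at 15.75 mg/kg even under the fast taper assumed here. The 13.5 mg/kg cut lies between them, so for children dosed as Table 1 and 7.1.10 suggest, the dose group nearly equals the response/MAP group.

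**4. Response imbalance.** Section 3.5 reports that ultra-low-risk children (65%) had "higher response rates (96% vs 47%, p<0.001) than other patients". As a check, 0.65 × 0.96 + 0.35 × 0.47 = 0.79, the overall response given in 3.4. Taking these groups as stand-ins for low and high dose, non-response is 4% against 53%, a gap of 0.49.

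**5. Gap with zero steroid effect.** If not being in response worsens a PROMIS score by D points (D is an assumption; the plan gives none), the day-28 gap is 0.49 × D:

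- D = 5: 2.5 points
- D = 10: 4.9 points
- D needed to reach 5 points: 5 / 0.49 = 10.2, about one SD, since the plan equates 5 points with half an SD

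**6. Precision.** With the expected 33 and 17 patients and SD 10, the standard error is 10 × √(1/33 + 1/17) = 2.99, and the 95% interval is ± 1.96 × 2.99 = ± 5.9 points. This is before losing children under 5, who complete no PROs.

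**7. Responders available.** 33 × 0.96 ≈ 32 in the ultra-low-risk group and 17 × 0.47 ≈ 8 among the others.

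**The case against.** The plan is more modest than a causal analysis. QOL and growth are exploratory (4.3, 4.7), 14.3 disclaims formal comparisons, and its dose groups are conditional and not stated to be cut at 13.5 mg/kg. Sections 4.2 and 14.3 already provide for reporting in the ultra-low-risk subset, which is defined by response and MAP. All of this stands and lowers the weight of the point. It does not remove it: subset reporting does not adjust the dose contrast, 14.3 goes on to plan a group comparison and a model, and 3.6 still states the steroid-effect aim.

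Dose group is also not the same as active disease. On the preliminary figures 47% of the other patients respond by day 28; a MAP above 0.29 removes a child whatever the clinical response; physicians may raise doses for other reasons; and under 9.1.1 second-line therapy scores as no response regardless of organ staging. This stands too: the groups differ in GVHD course on average, not child by child.

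Finally, the obvious statistical remedies have costs. Restricting to day-28 responders, or adjusting for GVHD stage at the visit, conditions on variables that dose may itself affect, with about 8 responders expected outside the ultra-low-risk group. That rules them out as the main analysis.

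**Conclusion.** The point holds: the dose-group contrast mixes GVHD course with any steroid effect, and the planned model cannot separate them. The near-coincidence of dose group and response group follows from the plan's own schedule, provided that removed patients are dosed roughly as suggested. The direction of the bias needs only that active GVHD worsens QOL, which 3.6 supports. Its size is unknown: 2.5 to 4.9 points at day 28 rests on an assumed 5 to 10 point effect of response and on preliminary patients grouped by risk, not by dose. No figure is available for days 90 and 180.

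Three stronger readings are tempting and are not supported:

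- A reader might infer that the contrast shows severity instead of steroid harm. It may contain both.
- A reader might infer that the predicted benefit will appear even without a steroid effect. The assumed gap stays below 5 points, and an interval of ± 5.9 points could easily miss it.
- A reader might infer the same bias for growth velocity. The documents give no mechanism or size for GVHD response altering height over the follow-up defined in 9.1.12.

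The primary endpoint is unaffected. The change is still worth making, because it alters what the QOL data can be said to show.

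**What to change.** In 14.3:

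- Label the dose-group contrast descriptive, and state that dose was assigned by clinical response and MAP. For growth velocity, only this item applies.
- Remove the steroid-effect reading here and in 3.6.
- Reconcile the statement that no formal comparisons are planned with the group comparison and model that follow it.
- Adjust any dose-group model for baseline PRO score, age and baseline GVHD grade.
- State the exposure window: cumulative dose through day 28 for day-28 PROs, and through day 90 for day-90 and day-180 PROs. Dose is not collected after day 90, so day-180 exposure stays incomplete, and the text should say so.
- Show PROs for ultra-low-risk versus other patients beside the dose split.
- Keep any analysis among day-28 responders, or adjusted for GVHD stage at the visit, as a sensitivity analysis, with the reason given.

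The cost is SAP wording and a little more analysis. Baseline PRO, age, GVHD staging and steroid dose to day 90 are already collected (8.1 and Table 2), so no visit, sample or treatment changes. The downside is a weaker exploratory claim.

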
## 15.0 DATA AND SAFETY MONITORING

The safety of subjects is paramount and supersedes all other concerns. This study employs several layers of oversight to ensure that patient safety is protected.

1. The Protocol Committee, composed of the individual site PI's, will review all facets of study conduct at all sites on monthly webinars
2. The Tisch Cancer Institute Data and Safety Monitoring Committee (TCI DSMC) of the Mount Sinai Health System is the DSMB of record for this study. The DSMB will be compliant with the NIH approved DSMP Charter. This committee will be responsible for monitoring the safety and data integrity of the trial. It is a DSMB entirely composed of members with no connection to this clinical trial.
3. Annual reviews and safety reporting will be provided to the single IRB and to each participating site.

**Protocol Committee safety reviews:** The centers participating in this study are collaborating centers in MAGIC (Mount Sinai Acute GVHD International Consortium). The local site principal investigator, data manager, and study coordinator will participate in monthly webinars where all facets of study conduct (e.g., screening rate, accrual, AEs, SAEs, and deviations) are discussed,

as is MAGIC standard practice, thereby facilitating early recognition and troubleshooting of potential problems.

The MAGIC Data Coordinating Center is responsible for collating all data and safety reports from all the participating sites, and providing the information to the TCI Data Safety Monitoring Committee.

**TCI DSMC:** The TCI DSMC serves as the data and safety monitoring board (DSMB) for investigator initiated studies conducted under the auspices of the Tisch Cancer Institute (TCI) at the Mount Sinai Health System. It is compliant with the National Institutes of Health and National Cancer Institute charter for DSMBs. This board will be responsible for monitoring the safety and data integrity of the trial and the DSMB for this study will be entirely composed of members with no connection to this clinical trial.

### **15.1 Multisite Clinical Monitoring Procedures**

This clinical study will be coordinated by the MAGIC Data Coordinating Center (DCC). As such it will be conducted in accordance with the ethical principles that are consistent with Good Clinical Practices (GCP) and in compliance with other applicable regulatory requirements.

Prior to subject recruitment, a participating site will undergo a site initiation meeting to be conducted by the DCC. This will be done as an actual site visit, teleconference, videoconference, or web-based meeting after the site has been given access to the study database and assembled a study reference binder. The site's principal investigator and his/her study staff will attend the site initiation meeting. Study-related questions or issues identified during the site initiation meeting will be followed-up by the appropriate DCC personnel until they have been answered and resolved.

This study will be monitored by a representative of the MAGIC Data Coordinating Center. Monitoring visits, whether remote or in person, will be made during the conduct of the study and at study close-out. The following issues will be monitored.

- Signed and dated ICF and assent
- Adherence to the protocol
- Completeness and accuracy of study data and laboratory samples collection

Any issues identified during these visits will be communicated to the site and are expected to be corrected by the site in a timely manner. For review of study-related documents at the DCC, the site will be required to ship, fax, or email documents to be reviewed, ensuring compliance with HIPAA and other privacy regulations.

Participating sites will also undergo a site close-out upon completion, termination or cancellation of a study to ensure fulfillment of study obligations during the conduct of the study, and that the site Investigator is aware of his/her ongoing responsibilities.

